Creation of a Data Safety and Monitoring (DSM) Plan. A DSM Plan will be formed in the early months of the project and be given responsibility to review and approve the study methods and the analysis plan for all study aims. The DSM Plan will be organized by Drs. [name] and [name] will include the PIs at each institution and key Coalition members with related experience (including health services researchers, methodologists, patients, social workers and biostatisticians). The DSM Plan will consist of annual teleconferences. At these meetings the study protocol, procedures, and any issues of concern related to research integrity will be discussed. Email correspondence or teleconferences between study sites may be arranged for any late-breaking issues. In addition, monthly monitoring of data is in place to ensure the assessment of data accuracy. The Principal Investigator assumes responsibility for assuring that the study is carried out in accordance with the DSM Plan. We will follow Emory University IRB protocols to ensure patient safety as we plan on external study sites will be relying on Emory's IRB. All patient data from each study site will be stored on a password-protected and encrypted computer, within a locked office and building. Only the PIs, project coordinator, and the data analyst will have access to any identifiable patient data throughout the study period.

Participant Recruitment and Study Inclusion/Exclusion Criteria.

Patient Recruitment Methods. To ensure that we target patients who are most likely to be medically eligible to receive a transplant, and yet also target patients as early in the transplant process as possible, a rigorous screening process will be utilized to screen patients who have been referred for transplant evaluation.

We will recruit participants by posting flyers in each of the four study sites, instructing those who are interested to contact the project coordinator via a telephone number to be secondarily screened for participation. To ensure that we target patients who are most likely to be medically eligible to receive a transplant, components of the eligibility criteria (AA or Black and age 18-70 years) will be posted on the flyer. Each transplant center will have its own flyer with appropriate contact information for that center. Please see attached flyer for further details.

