- 1) **Usual Care**, which involves the provision of standard transplant education procedures at each transplant center, which entail reviewing a packet of information with the pre-transplant coordinator. While there are some minor differences in the educational information about transplant that patients receive at each study site, the overall purpose is the same: the packet serves to inform transplant candidates and their families about the option LDKT. In addition, participants will be provided an iPad/tablet to watch a 10-minute National Kidney Foundation videos about kidney disease and transplantation in their private room during their regularly scheduled KT evaluation. This video discusses information about transplant, but does not specifically address LDKT and is not culturally sensitive to the AA population (<https://www.kidney.org/atoz/content/kidneytransnewlease>).
- 2) **Living ACTS website**, this involves the same procedures as above but also visiting the Living ACTS website and watch the Living ACTS video (embedded in the website). Participants will be given a time minimum to explore the website, as determined by the results in the individual interviews testing the intervention website. (<https://www.projectlivingacts.org>).

Randomization. At each site, patients will be randomized to usual care or the Living ACTS website individual-level intervention immediately following study consent and completion of the baseline measures using a simple, 1:1 randomization scheme. A random number generator program will designate patients' study arm assignment. Randomization only applies to the individual-level intervention; clinical providers across both study conditions will utilize the health systems intervention, T-REX, to communicate with one another about patients' transplant status. Once the patient has been assigned an arm from randomization, he or she will be

sent an email with the appropriate website. Once the patient receives the website, the coordinator will ask the patient to view the content. The coordinator will record the amount of time the patient viewed the website.

Blinding. The project coordinator is not blind to study condition. However, the coordinator will not be involved with the main outcome analyses, and analysts will be blind to condition.

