Immediate Follow-Up Survey. Participants will complete the immediate follow-up survey ((via HIPAAcompliant SurveyMonkey software), which will be a shortened version of the baseline survey that omits the demographic questions. Again, patients will have the project coordinator read the survey out loud and the coordinator will complete the survey. Participants will then be offered \$30 e-gift card as compensation for their participation. Please see attached immediate follow-up survey for further details.

Time. The entire intervention is expected to take 1 hour and 30 minutes for each patient from start to finish.

Coordinator Training. This project coordinator will undergo rigorous training by the principal investigators, have strong oversight from study staff, and submit regular documentation to study staff on recruitment progress.

Recruitment Timeline. Participant recruitment will occur in a staggered fashion across study site, starting with the main study site, to ensure that study investigators can make any necessary minor modifications to the study protocol.

Measurement. Covariates and key outcome measures are described below and in Table 2.

Independent Variable.

The primary independent variable is study arm (National Kidney Foundation kidney education video vs. Living ACTS)

Outcome Variables.

There are several key endpoints that will be examined in this study. **Primary Outcome:** The percent of patients with at least one living donor inquiry over 12 months

Secondary Outcomes: Psychosocial measures of knowledge, motivation, and self-efficacy for the behavioral skills to discuss LDKT with others

Table 2. Outcome measures for randomized controlled trial (Aim 2)

THEORETICAL CONSTRUCT	MEASURE (Scale Name)	DESCRIPTION	SAMPLE ITEMS
Information	Knowledge of opportunities for and risks of living donor transplant. ⁶⁸	This 25 item instrument assesses respondent's basic understanding of the opportunities for and the benefits and risks of living donor transplant. Response choices are true and false.	
 The likelihood of immediate function of the kidney from a living donor is excellent. Most donors must remain in the hospital for 10 days after surgery.

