entered as covariates in subsequent analyses. We note that detected differences may be site-specific and will explore site stratifications if we observe differences. Multivariable modeling techniques will be employed, if necessary, to correct for lack of balance in demographic or clinical characteristics between the two groups. For the main outcome, we will use generalized linear mixed models (GLMMs) for adjusted analyses of the data, specifying the logit link function for the binary outcomes (i.e. at least one living donor inquiry over 12-month period). Treatment group will be the independent variable of primary interest, modeled as a fixed effect with the control group specified as reference group. We will also include fixed effects for any potential confounding covariates noted in bivariable analysis. A random intercept will be considered to increase generalizability of results. To control for potential contamination bias over the course of the study, we will consider controlling for time of study entry.

We will pursue a similar modeling technique as described above for secondary analyses except that change in each of the three dependent variables will be the continuous (vs. binary) outcomes. We will conduct exploratory analyses where we assess change in behavioral intentions and comfort in initiating conversations about LDKT as outcomes. All data will be analyzed by the program coordinator for the study at Emory University with the oversight of Drs. [name] and [name], who will be blinded to study allocation. SAS 9.3 (Cary, NC) will be used for all analyses.

C.5. Specific Aim 3: To conduct a process evaluation of the newly created web-based Living ACTS intervention by adapting commonly used process evaluation constructs (reach, recruitment, fidelity, dose delivered, dose received, and context) for an online environment In Table 3 we describe what data will be collected, how, and when. **Table 3.** Process evaluation components and measures (Linnan & Steckler, 2002)

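### The SAP gives all analysis to an undefined program coordinator, probably the unblinded project coordinator, so the promised analyst blinding is not secured

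*Combined protocol and SAP*

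**What the plan says.** Four places in section C.4 bear on who analyses the data and what that person knows.

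- **Statistical Analysis Plan, last paragraph:** "All data will be analyzed by the program coordinator for the study at Emory University". Two named investigators oversee this work, and the sentence ends by describing them: "who will be blinded to study allocation".
- **Blinding:** "The project coordinator is not blind to study condition". The next sentence adds that "the coordinator will not be involved with the main outcome analyses, and analysts will be blind to condition".
- **Randomization and Immediate Follow-Up Survey:** the coordinator asks the patient to view the assigned site, and "The coordinator will record the amount of time the patient viewed the website". At follow-up, "patients will have the project coordinator read the survey out loud and the coordinator will complete the survey".
- **Data Safety and Monitoring Plan:** "Only the PIs, project coordinator, and the data analyst will have access to any identifiable patient data throughout the study period". This lists a data analyst separately from the project coordinator. The SAP gives that analyst no task.

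**The concern.** The Blinding paragraph accepts that the person delivering the intervention must know the arm, and compensates by keeping that person away from the main outcome analyses. The SAP sentence appears to undo this. It covers all data, and therefore the primary outcome, and gives the work to someone with a coordinator title.

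What is at stake is the set of analysis decisions still open when the data arrive. The SAP leaves undecided whether to include a random intercept, whether to adjust for entry date, whether to stratify by site, and which confounders found in bivariable work join the model. An analyst who knows the arms can see which of these choices favours Living ACTS. Blinding the analyst is the direct protection against that, and the plan claims to have it.

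**Working it through.** No arithmetic applies, because the point depends on no figure in the plan. The check is a comparison of the texts under each reading of the two titles.

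1. **Is the program coordinator defined?** No. The title appears once, in the SAP. Elsewhere the person who recruits, takes consent, administers surveys and directs patients to the website is the project coordinator. That the two titles mean one role is a reasonable inference, but it is not stated.

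2. **Reading A: one role.** The Blinding paragraph describes an unblinded coordinator excluded from the main outcome analyses. The SAP has the same person analysing everything.
   - For the primary outcome this contradicts both the exclusion and the promise of blind analysts.
   - For the secondary outcomes the exclusion may not apply, since it names only the main outcome analyses. The promise of blind analysts is still broken, and the same person has also read out and completed the follow-up survey.

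3. **Reading B: two roles.** There is no direct contradiction. The Blinding paragraph's general statement about analysts would cover a separate program coordinator. Three gaps remain:
   - The SAP does not say who this person is or whether they have contact with participants.
   - Its own blinding clause, read naturally, describes the two overseers and not the person running the models. Blinded oversight does not blind the person overseen.
   - Nothing in the document describes coded arm labels, a restricted analysis file or any other means of masking.

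4. **Could the data reveal the arm?** Yes, so coded labels alone may not be enough. The control video lasts 10 minutes. Living ACTS participants follow the same procedures and also visit a website whose video is expected to run about 20 minutes, so recorded viewing time could separate the arms. The process evaluation also codes individual screen recordings of website activity and links them to questionnaire data.

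5. **Which choices are really open?** Baseline variables that differ by arm at p < 0.05 are to be entered, which is a rule. Leaving out patients found ineligible for transplant (expected to be about 25%, under Study Size Justification) is also stated as a rule. The open items are the random intercept, entry date, site stratification and confounders from bivariable work.

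6. **Can knowledge of the arm affect the primary outcome itself?** Hardly. It is whether a donor inquiry was logged, taken from a discrete record field supplied by each center.

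Under Reading A the stated blinding fails. Under Reading B it is promised but not secured.

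**The case against.** The best reply is that this is a loose job title. The document uses several coordinator titles, the Blinding paragraph already states the rule that analysts are blind, and a clause attached to two overseers is weak evidence that the analyst is unblinded. Much of this stands: the documents do not establish that the two titles are one role, and under the two-role reading nothing is contradicted. It does not remove the need to reconcile the passages, because the SAP is the text an analyst will follow, and on its natural reading it conflicts with the Blinding paragraph.

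The plan also has safeguards. The primary outcome is objective, oversight is blinded, and the monitoring group, which includes biostatisticians and methodologists, reviews and approves the analysis plan. These limit the harm. They do not say who runs the models or how that person is kept blind.

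A reader might go further and infer that an unblinded analyst inflates the type I error by some stated amount. The documents do not support this. Exchanging the arm labels reverses the sign of the estimated log odds ratio and leaves its standard error unchanged, so the two-sided p-value is the same. An analyst seeking the smallest two-sided p across models could therefore do so with arms coded A and B. Such inflation measures an unfixed model, which is a separate matter. Knowing the arms adds the ability to choose by direction, and the documents give no basis for sizing that.

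A reader might also count the exclusion of about 25% of patients as an analyst's option. The plan states it as a rule.

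**Conclusion.** The point holds as an unresolved conflict over who analyses the data and whether that person is blind. It is a direct contradiction if program and project coordinator are one role, which is likely but not certain. Otherwise it is an undefined role with no masking procedure behind a general promise. No numerical size can be given. The exposure is confined to the open model choices and, under the one-role reading, to secondary outcomes collected and analysed by the same unblinded person. It does not reach ascertainment of the primary outcome. The correction should be made before any analysis by arm, chiefly because it is nearly free and restores a safeguard the plan already claims.

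**What to change.** Reconcile the Statistical Analysis Plan, the Blinding paragraph and the Data Safety and Monitoring Plan by replacing the SAP sentence with text to this effect: the primary and secondary analyses are run by the study data analyst, who has no contact with participants and receives the arm coded A or B; variables that could reveal the arm (website viewing time, website satisfaction, coded screen recordings) stay out of the analyst's file until the primary result is locked; and the coordinator who delivers the intervention has no role in these analyses. Use the same role titles in all three places.

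If the program coordinator is in fact a separate, blinded person, the sponsor should say so in the SAP, with the same masking arrangements.

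The cost is a short SAP statement, a coded arm variable and a split of the data file. The data analyst role is already listed, so no new post should be needed.

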C.3. Specific Aim 1: To develop and refine a web-based version of Living ACTS. We will adapt our existing intervention for an online environment. The Internet provides an ideal mechanism for delivering Living ACTS. Because few DVD players exist in transplant centers, it supports the sustainability of the intervention beyond the life of the study. Additionally, patients can go home and watch the video with family, multiple times if desired. Finally, in a way that a DVD cannot, it affords the option to directly communicate with potential donors by sending an email and using other forms of social media (e.g., Facebook posts) to communicate the need for a LDKT.

Website & Video Development. We will be updating our existing WebACTS (HRSA-funded project) website (the web address for the test site is: <http://actnow.projectwebacts.org/#/>), which seeks to increase registration on the Georgia state donor registry. The new website will be similar to the look and feel of our existing website except that the current “ACT Now” tab that provides a mechanism for registration on the state donor registry will be replaced with an “ACT Now” tab that informs friends/family of LDKT as a viable treatment option for the patient. The website will also include the ability to pick from boilerplate messages about how to share via social media (i.e. Facebook, Twitter, Instagram) as well as traditional media (i.e. email and printed letter) with friends and families their need for a KT, and more information about LDKT (including a link to the Living ACTS website).

We will contract with Tomorrow Pictures, Inc., a film company we have worked with for the past 14 years, to refine the Living ACTS video. We anticipate shortening the video from 30 to 20 minutes and making minor edits using existing footage. The website will be hosted on the Emory server, which offers the benefit of a secure server free of charge and technical support from our existing Department of Information Technology. Our team of content area and research experts will work closely with them to provide feedback on graphical

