Transplant center administrative records. Because of their role in the recruitment process, the transplant coordinators will be able to easily get information on aspects of the environment that may have influenced delivery of the intervention as well as data on the proportion of eligible participant who could have been recruited into the study. These data will be collected retrospectively at the end of data collection at each transplant center by examining patient medical records and scheduling information.

Component	Definition	Measure	Data Source
Context	Aspects of the transplant center environment that may influence uptake of the intervention	-Description of the transplant education process -Description of the evaluation process -Number of annual LDKTs among AA patients	Transplant center administrative records
Reach	The proportion of the intended patient population that participates in the study	-Proportion of eligible participants who were recruited into the study	Transplant center administrative records
Dose received	The extent to which participants actively engage with the website	-Participant satisfaction with the website	Immediate follow-up survey
Fidelity	The extent to which the intervention was implemented as planned	-Number of times video starts/stops per person -Duration of time spent on website	Website usage statistics
Recruitment	Procedures used to approach and attract participants	-Proportion of screened individuals who consent to participation -Reasons for ineligibility	Study records & Transplant center records

Immediate follow-up survey of participants. The immediate follow-up survey will include a measure of satisfaction with the website to inform our understanding of the “dose received” as part of the process evaluation. This 10 item measure will include four items that ask participants to rate their satisfaction with the video (in terms of its quality, informative nature, length, and trustworthiness), four items that rate the website more generally (in terms of the ease at which one can find and understand information, visual appeal, and trustworthiness), and two general questions about recommending the website to others and an opportunity to provide general comments. Questions 1-8 will be used generate an overall satisfaction score that may be examined in relationship to other outcomes measured on the immediate follow-up measure.

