Website usage statistics. Our process evaluation will be informed by data collected via Google Analytics, which is a platform for measuring attributes of website usage⁷⁴, and “Record it!”, which is an application used

to record and monitor website usage. There is a broad array of variables we can use to assess use of the intervention website such as average time spent on each page, number of starts/stops of the video, and use of the social media functions (e.g., to e-mail friends/family). Google Analytics data will be used to assess group-level website usage (i.e. videos most watched, modules that participants spent the most time exploring, etc.). “Record it!” data, however, will provide individual-level website usage data in the form of video recordings of each participant’s website activity. Study staff will review each video and code participant website activity according to a pre-established code book. These individual reports will provide data that can then be linked to individual-level questionnaire data so that we can perform exploratory data analyses to determine whether individuals in the intervention condition who used certain functions of the website (e.g., e-mailing friends/family) also demonstrate greater change in the secondary outcomes (e.g., knowledge).

Study records. We will use a screening eligibility form to determine eligibility for participation in the study across all sites. One form will be used for each potential participant. All screening questions will be asked of all participants even if the response to an earlier question disqualifies a patient from participation so that we can collect accurate data on reasons for ineligibility.

D. Data Handling and Record Keeping

Human Subjects / Institutional Review Board Approval. The study will be conducted in a manner that protects the rights of all human participants. Moreover, each aspect of the study will only be implemented once the proper Institutional Authorization Agreements have been approved by Emory University and each site’s Institutional Review Board (Emory, Piedmont, Augusta, and Medical University of South Carolina).

Confidentiality. Information about study subjects will be kept confidential and managed according to the requirements of the Health Insurance Portability and Accountability Act of 1996 (HIPAA).

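### Group-level Google Analytics summaries will mix Living ACTS participants with family, friends and other visitors, because the site's link is built to be shared and no participant tag, login or filter is described

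*Combined protocol and SAP*

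**What the plan says.** Section C.5 (Website usage statistics) names two tools and gives each a role.

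- **Google Analytics** is the aggregate tool: "Google Analytics data will be used to assess group-level website usage". The examples that follow, such as the most-watched videos and the modules that took most time, are worded as participants' behaviour.
- **Record it!** is the individual tool. It "will provide individual-level website usage data in the form of video recordings of each participant", and the text continues to that person's website activity. Further, "Study staff will review each video and code participant website activity according to a pre-established code book", and "These individual reports will provide data that can then be linked to individual-level questionnaire data".

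Table 3 in C.5 lists two fidelity measures, "Number of times video starts/stops per person" and time on the website. It gives their source only as website usage statistics, the heading that covers both tools.

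Section C.3 (Website & Video Development) describes boilerplate messages that a patient may send by social media, email or printed letter. They offer "more information about LDKT (including a link to the Living ACTS website". The opening of C.3 also expects patients to watch again at home with family. Section C.4 gives one address for the Living ACTS site. Under Randomization, patients are emailed the website for their arm, and "The coordinator will record the amount of time the patient viewed the website".

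**The concern.** Google Analytics, as the plan describes it, summarises activity on a site. It describes participants only if participants are the only visitors or if their visits can be picked out. Neither condition is met here. The site is meant to reach people outside the trial, and the plan describes nothing that would distinguish a participant's visit from that of a relative who followed a shared link.

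The contamination also depends on the intervention. The more patients use the sharing feature, the more outside traffic arrives and the less the totals describe patients. A busy site could be read as strong engagement by patients when much of the activity is by their contacts, and the module rankings could reflect what potential donors want to know. The two kinds of traffic answer different questions, and both are of interest, but the plan would report them as one.

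**Working it through.** The plan gives no figure for website traffic, so there is none to reproduce. The check compares what each section says, followed by a scale illustration.

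**1. Who can visit the site?** Living ACTS participants, by emailed link (C.4, Randomization). Friends and family, by the link in the share messages (C.3). Family watching at home with the patient (C.3).

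**2. Does the plan separate them?** C.3, C.4 and C.5 describe no login, participant-specific link, traffic filter or time window. C.5 nevertheless words the aggregate output as participants' use.

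**3. Which measures are exposed?**

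| Measure | Named source | Exposed to outside visitors? |
|---|---|---|
| Group-level use (videos, modules) | Google Analytics | Yes |
| Individual use of site functions, linked to questionnaires | Record it! | No; each recording is of one participant |
| Session viewing time | Coordinator's record (C.4) | No |
| Video starts/stops per person; time on website (Table 3) | Website usage statistics, tool not specified | Only if taken from Google Analytics |
| Primary outcome | Transplant center inquiry records (C.4) | No |
| Secondary outcomes | Baseline and immediate follow-up surveys (C.4) | No |

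**4. How large could the mixing be?** Let k be the number of outside visits per participant visit. The documents do not give k, so it is an assumption. The non-participant share of visits is s = k/(1 + k):

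- k = 0.25: 0.25/1.25 = 20%
- k = 1: 1/2 = 50%
- k = 3: 3/4 = 75%

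**5. What does that do to a reported average?** If P is the mean of some per-visit usage measure among participants' visits and O the mean among outside visits, the site average is (1 − s)P + sO. It differs from P by s(O − P). At s = 50%, half of any difference between the two groups enters the figure reported for participants. If outsiders use the site exactly as participants do, averages are unbiased, but visit counts and total time are still inflated.

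**6. Is the individual source workable?** The procedures for Record it! appear only in the Aim 1 face-to-face interviews (C.3). In the trial, C.1 has patients enrolled by Zoom or telephone and C.4 sends the website by email. The Aim 2 text on eligibility, consent, delivery and follow-up does not mention Record it!. The statement of Aim 3 in the opening specific aims lists it as a data source, while the parallel statement under Objectives does not.

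**The case against.** The best defence is that the plan already divides the work properly. Google Analytics is used only for aggregate description. The sentence that follows assigns individual usage to Record it!, with coding and linkage to questionnaires, and refers to people in the intervention condition, so trial participants are meant. The coordinator separately records viewing time. The planned exploratory analysis relates individual use to change in the secondary outcomes, which are measured at the immediate follow-up survey, so later visits by anyone cannot enter it. All of this stands, and it confines the point to the aggregate summaries.

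It also rules out several stronger readings that a reader might infer:

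- *That the per-person fidelity measures have no valid source.* Two are named. What is missing is an account of how Record it! operates in a remote session, which is an operational gap in a named source.
- *That participants are told to share the link.* C.3 describes an available feature, and in C.4 the coordinator asks the patient only to view the content.
- *That all randomised patients receive the same address.* Each arm is sent its own website, so the issue concerns the Living ACTS site.
- *That Aim 3 could then not help to interpret Aim 2.* Only the fidelity row of Table 3 draws on website statistics, and the individual data are a separate stream.

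The defence does not cover the aggregate output itself, which is still labelled as participants' use with no means of making it so.

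**Conclusion.** The point holds for the group-level Google Analytics summaries. As written, the plan will attribute to participants an unknown amount of use by other people. The 20% to 75% range above rests entirely on assumed values of k and shows sensitivity; it is not an estimate. The conclusion also assumes that no login or filter exists outside the published text.

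A smaller related gap is that Table 3 does not say which tool feeds each fidelity measure, and the Aim 2 procedures do not explain how Record it! is run by Zoom or telephone. Neither matter touches the primary or secondary outcomes. This is an inexpensive improvement to a process evaluation. It is worth making before recruitment because traffic collected without tags cannot be sorted later.

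**What to change.** 1. Email Living ACTS participants a link that carries a participant tag. A non-identifying code is enough, since individual usage comes from elsewhere.
2. Give the links in the share messages a different tag, including the address printed in the letter version.
3. In C.5, restrict the group-level Google Analytics summaries to participant-tagged traffic, report share-tag visits separately, and label any untagged total as all-visitor traffic.
4. In Table 3, state that starts/stops per person and time on the website come from Record it! and the coordinator's record. In the Aim 2 procedures, describe how Record it! is run in a Zoom or telephone session. Make the two statements of Aim 3 data sources agree.

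The cost is a small change to the links and the analytics set-up, and possibly a sentence in the consent. Some misattribution will remain: a participant may forward the tagged link, watch with family on it, or type the plain address. It should be slight compared with having no separation at all.
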